6.1 Inclusion Criteria

Subjects must meet the following inclusion/exclusion criteria to be eligible for the study.

- 1 Age \geq 18 years.
2. Patient must have a documented diagnosis of MDS according to World Health Organization (WHO) criteria (see Appendix IV) or non-proliferative chronic myelomonocytic leukemia (CMML) (WBC \leq 12,000/uL).
3. Patients must have International Prognostic Scoring System (IPSS) categories of Low- or Intermediate-1-risk disease (see Appendix 4).
4. Patients must have symptomatic anemia untransfused with hemoglobin \leq 10.0g/dL within 8 weeks of registration or with RBC transfusion-dependence (i.e., \geq 2 units/month) confirmed for a minimum of 8 weeks before randomization. Or patients have platelet $<$ 50,000/uL with hemoglobin $>$ 10.0 g/dL.
5. Patients must have IPSS score determined by cytogenetic analysis prior to randomization. Patients with cytogenetic failure and \leq 10% marrow blasts will be eligible.
6. Patients must be off all disease modifying therapy for MDS for 28 days prior to initiation of study treatment. Patients may receive hydrocortisone prophylactically to prevent transfusion reactions.
7. Patients must not have documented iron deficiency. All patients must have documented marrow iron stores. If marrow iron stain is not available, the transferrin saturation must be \geq 20% or a serum ferritin \geq 100 ng/100 mL or soluble transferrin receptor $<$ 5mg/L.
8. Women must not be pregnant or breastfeeding. Females of childbearing potential should have 2 negative pregnancy tests (sensitivity of at least 50 mIU/mL). The

first test should be performed within 10-14 days, and the second test within 24 hours prior to prescribing lenalidomide.

9. Females of reproductive potential must adhere to the scheduled pregnancy testing as required in the Revlimid REMS® program. Able to take aspirin (81 or 325 mg) daily as prophylactic anticoagulation (patients intolerant to ASA may use warfarin or low molecular weight heparin).

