8.2 SUPPORTIVE CARE

1. All supportive measures consistent with optimal patient care will be given throughout the study.

2. Therapies considered necessary for the patient's well being may be administered at the discretion of the Investigator. These therapies include antibiotics, analgesics, antihistamines, or other medications, and transfusions of red blood cells, platelets, or fresh frozen plasma given to assist in the management of complications associated with MDS or study treatment.

3. Packed RBCs: Transfusions of two units of packed RBCs should be considered for decline in hematocrit (HCT) to $< 25\%$ or symptoms of cardiovascular compromise. The following **transfusion thresholds and guidelines** are recommended for study participants: HCT $< 25\%$, two units of packed RBCs; HCT $< 21\%$, three units of packed RBCs; HCT $< 18\%$, four units of packed RBCs.

4 Platelets: Eight to ten units of random donor platelets or one cytopheresis unit of single donor platelets should be administered to all subjects with signs of hemostatic failure (i.e., bleeding or petechiae) or life threatening thrombocytopenia (i.e., platelet count $< 10,000/\mu\text{L}$).

5 Patients should not receive androgens or steroids for supportive treatment of their anemia or thrombocytopenia

6 Patients may receive hydrocortisone prophylactically to prevent transfusion reactions. Steroids given for adrenal failure, hormones administered for non-cancer related conditions (e.g. insulin for diabetes), and intermittent uses of dexamethasone as an antiemetic are permitted concomitantly with study drug. Short courses of steroids to treat study drug-induced skin rashes are also permitted.

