- o For patients with 20% to 30% blasts: > 50% increase to 30% blasts

Any of the following:

At least 50% decrement from maximum remission/response in granulocytes or platelets

Reduction in Hgb by 2 g/dL

Transfusion dependence

7. Disease Transformation

Transformation to AML (> 30% blasts).

Cytogenetic Response

Requires 20 analyzable metaphases when using conventional techniques. Analysis of data will require 20 metaphases before and after treatment. Fluorescent *in situ* hybridization (FISH) may be used as a supplement to follow a specifically defined cytogenetic abnormality, but it is not a substitute for conventional cytogenetic studies.

Cytogenetic response is defined as follows:

Complete response: Restoration of a normal karyotype in patients with a documented pre-existing clonal (>2 metaphases abnormal) chromosome abnormalities.

Partial response: > 50% reduction in the percentage of bone marrow metaphases with only clonal abnormality.

Hematologic Improvement

Improvements must last >8 consecutive weeks.

1. Erythroid Response

Hgb increase by 1.5 g/dL if not transfusion dependent Relevant reduction of units of RBC transfusions by an absolute number of at least 4 RBC transfusions/8 wk compared with the pretreatment transfusion number in the previous 8 wk. Only RBC transfusions given for a Hgb of 9.0 g/dL pretreatment will count in the RBC transfusion response evaluation

2. Platelet Response

For patients with a pretreatment count < 100,000/mm³, an absolute increase of > 30,000/mm³ (for patients with pretreatment counts >20,000).

For patients with pretreatment counts < 20,000, an increase to absolute count above 20,000 by at least 100% increase will be considered as response.

†;for platelet transfusion-dependent patients, stabilization of platelet counts and platelet transfusion independence.

3. Neutrophil Response

At least 100% increase and an absolute increase $> 0.5 \times 10^9/L$

4. Progression/Relapse Following Erythroid Hematologic Improvement

At least 1 of the following:

At least 50% decrement from maximum response levels in granulocytes or platelets

Reduction in Hgb by 1.5 g/dL

Transfusion dependence

Duration of Response

Time to disease progression (as per Bone Marrow Responses above) or progression/relapse following hematologic improvement (as per Hematologic Improvement above).

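### Entry counts every transfused unit but the erythroid response rule does not, so some transfusion-dependent entrants cannot meet that rule even if transfusion stops

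*Combined protocol and SAP*

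**What the plan says.** **Entry.** Inclusion item 4 in Section 6.1 has a transfusion route: two or more "units/month) confirmed for a minimum of 8 weeks before randomization". It sets no Hgb condition on those units. Item 4 also admits untransfused patients with Hgb of 10.0 g/dL or less, and patients with platelets below 50,000/uL and Hgb above 10.0 g/dL.

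**Response.** Section 11, Erythroid Response, has two routes:
- Hgb: "Hgb increase by 1.5 g/dL if not transfusion dependent".
- Transfusion: a reduction "by an absolute number of at least 4 RBC transfusions/8 wk compared with the pretreatment transfusion number in the previous 8 wk". This is followed by the counting limit: "Only RBC transfusions given for a Hgb of 9.0 g/dL pretreatment will count in the RBC transfusion response evaluation".

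Both carry the durability condition "Improvements must last >8 consecutive weeks".

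**Decision rule.** Section 14.2 stops the trial if fewer than 7 of the first 25 patients respond and declares success at 17 or more of 52. It names major erythroid response as the primary outcome, a term Section 11 does not define. Section 4.1.1 gives hematologic improvement (HI) as the primary efficacy objective.

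**The concern.** The entry minimum and the required fall are the same number, about 4 units per 8 weeks, but they count different things: entry counts all units, response only those within the Hgb limit. A patient near the minimum has no slack. One uncounted unit makes the transfusion route arithmetically impossible, and the Hgb route is reserved for patients who are not transfusion dependent. A patient who becomes fully transfusion independent is then scored an erythroid non-responder.

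The trial has a single go/no-go rule and no randomized control. If Section 11's erythroid rule supplies the responses for that rule, such patients stay in the denominator without any chance of entering the numerator, and a useful treatment is more likely to be rejected.

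**Working it through.** **1. The counting conflict.** Let C be the countable pretreatment units and T the on-study units per 8 weeks. The transfusion route needs C − T ≥ 4. Since T cannot be below 0, C must be at least 4.
- Entry minimum: 2 units/month × 2 four-week months = 4 units in total (about 3.7 with calendar months).
- One of 4 units outside the limit: C = 3, so the largest possible fall is 3 − 0 = 3, below 4.
- Transfusion in two-unit steps, as the Section 8.2 guidance describes: one episode outside the limit leaves C = 2.

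**2. Who is exposed.** Assume two-unit episodes, each given above 9.0 g/dL with independent probability q. The documents give no value for q. A patient is blocked if fewer than two episodes are countable.

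| Pretreatment units | Formula | q = 5% | q = 10% | q = 20% |
|---|---|---|---|---|
| 4 | 1 − (1−q)² | 9.8% | 19% | 36% |
| 6 | q³ + 3q²(1−q) | 0.7% | 2.8% | 10.4% |
| 8 | q⁴ + 4q³(1−q) | <0.1% | 0.4% | 2.7% |

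The problem sits almost wholly at the entry minimum. For 5% of all patients to be blocked at q = 10%, about 5/19 = 26% of the trial would have to enter at 4 units; for 10%, about 10/19 = 53%. At q = 20% the figures are 5/36 = 14% and 10/36 = 28%. At q = 5%, blocking 10% of all patients cannot come from 4-unit entrants alone (10/9.8 exceeds 1).

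**3. The plan's own figures.** Under the written rule,

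P(accept | p) = Σ over x = 7 to 25 of Bin(x; 25, p) × P(Bin(27, p) ≥ 17 − x).

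- p = 0.25: 0.118, against a stated maximum of 0.10.
- p = 0.40: 0.856, against a stated 0.80.
- Expected sample size at p = 0.25: 25 + 27 × (1 − 0.561) = 36.9, against a stated 32.4.

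Stopping at 7 or fewer gives 0.099, 0.800 and 32.4, which matches. The stage 1 boundary is therefore a separate problem, unrelated to transfusion counting. Both versions are shown below.

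**4. Effect of blocked patients.** If a fraction f of all patients cannot respond, and would otherwise have responded at the same rate as the rest, a true 40% rate is observed as 0.40 × (1 − f).

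| f (assumed) | Observable rate | P(accept), stop if fewer than 7 (as written) | P(accept), stop at 7 or fewer |
|---|---|---|---|
| 0 | 40% | 85.6% | 80.0% |
| 5% | 38% | 78.4% | 72.3% |
| 10% | 36% | 69.4% | 62.9% |

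**The case against.** **Which outcome governs.** The strongest objection is that the documents do not settle whether the Section 11 erythroid rule feeds the 7/25 and 17/52 counts. The only description of major erythroid response is in the background (Section 3.4), for an earlier study: sustained transfusion independence or a Hgb rise above 2 g/dL, with no 4-unit rule and no 9.0 limit. On that description the blocked patient who stops transfusion is a responder. If HI governs, platelet or neutrophil improvement remains open. This stands, and it makes the effect on the decision conditional. It does not remove the conflict, because Section 11 states that its criteria will be used to assess response. A reader might infer that these patients can never respond at all; the documents support that only for the Section 11 erythroid rule.

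**Reclassification.** The erythroid criteria do not define transfusion dependence, so a patient with few countable units might be moved to the Hgb route. That is possible but unstated. The only numeric definition in Section 11, under relapse, is more than 2 units in 8 weeks, which a 4-unit patient exceeds.

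**Size.** The 5% and 10% shares are not derived from the documents, and item 4 admits many patients by other routes. This also stands.

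**A tempting stronger reading.** Section 8.2 says "Transfusions of two units of packed RBCs should be considered for decline in hematocrit (HCT) to" below 25%, and a reader might infer that a lower on-study trigger turns non-responders into responders. The documents do not support this:
- They give no hematocrit-to-Hgb conversion. At assumed Hgb/HCT ratios of 0.32 to 0.36, 25% is 8.0 to 9.0 g/dL, so there may be no gap.
- The threshold is a recommendation beside cardiovascular symptoms, and supportive therapies "may be administered at the discretion of the Investigator".
- The 9.0 limit already removes pretreatment units given above it.
- Assume two units raise Hgb by 2 g/dL, followed by exponential decline with a time constant of 3 to 10 weeks. A patient settling at 8.5 g/dL would then need about 1.0 to 3.3 units per 8 weeks at a 9.0 trigger. That is usually too few to score a fall of 4.

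If on-study units are counted without the limit, the asymmetry works against response.

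**Conclusion.** The concern holds for the Section 11 erythroid rule. Item 4 admits transfusion-dependent patients who, at or near the minimum, cannot meet that rule if even one pretreatment unit falls outside the 9.0 g/dL limit. This follows from the text alone, given the reading of 9.0 or below.

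The consequence for the trial decision depends on that rule supplying the responses. If it does, the bias is toward rejecting the treatment: at a true 40% rate, a loss of about 7 percentage points of acceptance probability for 5% blocked (85.6 − 78.4 = 7.2) and about 16 points for 10% (85.6 − 69.4 = 16.2). Those shares are assumptions, and the true share could be smaller. No inflation of false acceptance through a changed transfusion trigger is claimed. The point deserves correction because the conflict is certain, the fix is cheap, and pre-transfusion values that are not recorded at the time may be hard to recover.

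**What to change.** 1. In item 4, for the transfusion-dependence route, require at least 4 units in 8 weeks that meet the Section 11 counting limit, so that every patient entered by this route can respond.
2. Restore or state the comparison sign in Section 11, and say that the same counting rule applies to the pretreatment and on-study windows.
3. Record the pre-transfusion Hgb for every unit in both windows. The schedule in Section 2 lists only transfusion history; the case report form is not in the documents, so the field may already exist.

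Item 4 and Section 11 must be reconciled with each other; no transfusion threshold is proposed. The cost is amended wording and at most one data field. A few candidates with undocumented or higher-trigger transfusions would no longer qualify by the transfusion route.

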3.2 Treatment of Thrombocytopenia in MDS or sAML/MDS

In a review of patients with MDS referred to the M. D. Anderson Cancer Center, the incidence of life-threatening thrombocytopenia was 16-40% depending on the MDS risk status, with a median survival of only 6 to 12 months. The incidence of thrombocytopenia increases with disease progression, and without effective therapies, some patients may experience life-threatening bleeding(1)

In MDS, the disease clone includes the megakaryocytic lineage. Megakaryocytes from patients with MDS show impaired proliferation and differentiation, thus causing thrombocytopenia (2). Additional aspects potentially contributing to thrombocytopenia in MDS are premature cell death of megakaryocytes and decreased platelet life span(3). Interestingly, these aspects can be observed in both patients with MDS, and patients with Idiopathic Thrombocytopenic Purpura (ITP). In MDS, the megakaryocytic proliferation is unresponsive to recombinant thrombopoietin (TPO), possibly due to deregulated TPO-receptor-mediated signaling(4) . In addition to the qualitative disturbance of the TPO-receptor, there is also a quantitative disturbance in terms of the number of TPO receptors, which show a reduced expression by 50% on MDS platelets, as well as on CD41+ and CD34+ cells as compared to normal cells. However, an in vitro study showed that CD61+ cells in suspension cultures increased with PEG-rHuMGDF (pegylated recombinant human MGDF)alone in 31 out of 39 patient samples from MDS patients (5). The clinical development of PEG-rHuMGDF was aborted owing to the development of cross-reacting autoantibodies against endogenous TPO. More recently, Phase II data were presented for another TPO-R agonist, romiplostim, which showed efficacy in 41% of the patients with low- or intermediate-1 risk MDS (6) However, few patients showed some direct or indirect evidence for disease progression [FDA Oncology Drug Advisory Committee Meeting, March 2008].

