4 STUDY OBJECTIVES AND ENDPOINTS

4.1 Objectives

4.1.1 Primary Objectives

- To evaluate the rate of hematologic improvement of the eltrombopag/lenalidomide combination (as per Modified IWG criteria)
- To evaluate the safety and tolerability of the combination

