5 INVESTIGATIONAL PLAN

5.1 Overall design

This is a multicenter, Phase II study evaluating the efficacy and safety of the combination of lenalidomide and eltrombopag in low risk MDS. This study will include patients with low risk MDS (IPSS low and Int-1) with symptomatic anemia or transfusion dependence. Patients will be treated in 2 separate arms based on their baseline platelet counts:

Arm A : Patients with platelet counts $\geq 50k$ at baseline:

These patients will start Len at 10mg/d for 3 weeks/month, and will not start Eltrombopag until the platelet counts drop below 50,000. If platelets drop less than 50,000, Len will be stopped and Eltrombopag will be started at a dose of 100mg initially and titrated up (similar schema to 509 study) to achieve a platelet count above 50,000. Once the platelet count above 50,000 is achieved, the same dose of Eltrombopag will be continued for an additional two weeks. Once a platelet count $> 50,000$ is maintained for two weeks, Eltrombopag will be discontinued and Len will be started as a single agent. If the plts again fall below 50k then Len will be stopped and Eltrombopag will be re-initiated at the dose that was last given to the patient. Once the platelets are increased to above 50,000 and maintained at this level for 2 weeks, Len will be started again and this time will be given concurrently with Eltrombopag. These agents will now be used concurrently for all subsequent cycles.

Arm B: Patients with Plts $< 50k$ at baseline

These patients will not receive Len initially. Eltrombopag will be started alone at a dose of 100mg initially and titrated up (similar schema to 509 study) to achieve a

platelet count above 50,000. Once the platelet count above 50,000 is achieved, the same dose of eltrombopag will be continued to additional two weeks. Once the plt count > 50,000 is maintained for two weeks, the patients will discontinue eltrombopag and follow the treatment algorithm described for patients in arm A. Patients that never drop their platelet counts below 50,000 will not receive any additional eltrombopag. (Figure 1)

Treatment with myeloid growth factors is permitted for the management of neutropenia at the discretion of the treating investigator.

Study drugs will be continued until disease progression or unacceptable toxicities.

Bone marrow examinations will be performed at baseline, at every 4 months and at study discontinuation.

52 evaluable adult subjects with MDS will be evaluated.

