14.2 Sample size and power considerations

The primary outcome is major erythroid response. A maximum of 52 patients will be enrolled into the study. An early stopping rule for lack of efficacy will be implemented as follows based on Simon's optimal two-stage design. After the first 25 patients have been enrolled and evaluated for response, the trial will be terminated early if fewer than 7 patients respond to treatment. If 7 or more responses are observed, the trial will continue until a total of 52 patients have been evaluated. At the end of the trial, the treatment will be considered efficacious and worthy of further study if 17 or more patients respond out of 52 patients.

The target response rate is assumed to be 40%. (Conservative estimate) A response rate less than 25% is considered to be clinically unimportant(21). Under these assumptions, the design specified above has the following operating characteristics. The probability of accepting the treatment for further study if the response rate is unacceptably low

(<25%) is at most 10%. In contrast, there is a 80% probability of accepting the treatment for further study if the response rate is at least 40%. The expected sample size is 32.4 subjects. It is also assumed that 10-20% of patients with plts > 50,000 that receive Len may not need Eltrombopag at all as there plts will not fall below 50,000.

Furthermore, since we will accrue patients with both high and low platelet counts, it is possible that the response rates to Lenalidomide will be different in these groups. These will be analyzed by exploratory studies.

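### A platelet rise produced by eltrombopag alone can count as hematologic improvement of the combination, because the platelet criterion has no drug-exposure condition

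*Combined protocol and SAP*

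**What the plan says.** Section 4.1.1 gives the first primary objective as "To evaluate the rate of hematologic improvement of the eltrombopag/lenalidomide combination (as per Modified IWG criteria"). The synopsis lists hematologic improvement, without a lineage, as the primary endpoint. Section 14.2, which contains the two-stage rule, says instead: "The primary outcome is major erythroid response".

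Section 11 lists erythroid, platelet and neutrophil response under hematologic improvement and requires that "Improvements must last >8 consecutive weeks". The platelet rule depends on the pretreatment count:

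- Above 20,000 and below 100,000: an absolute rise of more than 30,000.
- Below 20,000: "an increase to absolute count above 20,000 by at least 100% increase will be considered as response".

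Neither rule mentions which drug the patient is taking. Complete remission, in the same section, counts platelets only when the patient is off thrombopoietic agents.

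Arm B (baseline platelets below 50,000) gets no lenalidomide at first. Section 5.1: "Eltrombopag will be started alone at a dose of 100mg initially and titrated up". Under Section 8.1.2, lenalidomide starts, and eltrombopag stops, only after untransfused platelets have been above 50,000 for at least 2 weeks. Patients without platelet recovery within 8 weeks of starting eltrombopag leave the study.

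**The concern.** The hypothesis in Section 3.1 is that eltrombopag lets patients tolerate lenalidomide for long enough to respond to it. A platelet rise during the eltrombopag lead-in does not test that, yet as Section 11 is worded it can contribute to the HI rate attributed to the combination. It can also bring forward the date of improvement, and time to HI is a secondary objective.

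Eligibility makes this more than theoretical. Section 6.1, criterion 4, admits patients with platelets below 50,000 and hemoglobin above 10.0 g/dL. They enter because of low platelets and begin in Arm B on eltrombopag alone.

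**Working it through.** **1. Count threshold against the lenalidomide gate.** For a baseline b below 20,000 the threshold is max(20,000, 2b). For b from 20,001 to 49,999 it is b + 30,000. The gate (Section 8.1.2) is a count above 50,000.

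| Baseline | Threshold | 50,000 minus threshold |
|---|---|---|
| 5,000 | 20,000 | 30,000 |
| 10,000 | 20,000 | 30,000 |
| 15,000 | 30,000 | 20,000 |
| 19,999 | 39,998 | 10,002 |
| 20,001 | 50,001 | −1 |
| 30,000 | 60,000 | −10,000 |
| 49,999 | 79,999 | −29,999 |

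Below 20,000 the threshold never reaches 40,000, so passing the gate always passes the count criterion. From 20,001 upward it does not guarantee this.

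**2. Duration.** Let c be the week in which the threshold is crossed and t the week in which 50,000 is first passed (t at most 8). Lenalidomide then starts at about week t + 2. Improvement completed before lenalidomide needs (t + 2) − c > 8, that is c < t − 6. With t = 8 this means c < 2; with c at or after week 0 it means t > 6. Example: baseline 12,000, above 24,000 from week 1, above 50,000 from week 8, lenalidomide at week 10. That is 10 − 1 = 9 weeks of improvement without lenalidomide. A patient who passes 50,000 at week 2 reaches the gate at about week 4, and the remaining weeks fall after the switch.

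**3. The plan's own design figures.** Section 14.2 states 25 then 52 patients, null 25%, target 40%, error at most 10%, power 80% and expected size 32.4. An exact binomial calculation gives these when the trial continues with 8 or more of 25: error 0.0992, power 0.8003, expected size 32.38. With the boundary as written (continue with 7 or more) it gives 0.1179, 0.8556 and 36.85. That discrepancy is a separate matter. The written boundary is used below, so the reference value is 11.8%.

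**4. What would happen if HI were put into the 17-of-52 rule.** Assumptions, none of them supplied by the documents for this purpose:

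- The true erythroid rate is 25%, the null.
- Platelet and erythroid response are independent.
- Arm B is a share s of 20%, 30% or 40% of patients.
- The Arm B platelet response q is 20% or 41%. The 41% is borrowed from Section 3.2, which describes another agent of the class: "romiplostim, which showed efficacy in 41% of the patients with low- or intermediate-1 risk MDS".

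Arm B rate = 1 − (1 − 0.25)(1 − q). For q = 0.41 this is 1 − 0.75 × 0.59 = 0.5575. The overall rate is 0.25 + s × 0.75 × q.

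| q | s | Overall rate | Chance of at least 7/25 and at least 17/52 |
|---|---|---|---|
| 0.20 | 0.2 | 0.280 | 0.244 |
| 0.20 | 0.3 | 0.295 | 0.324 |
| 0.20 | 0.4 | 0.310 | 0.410 |
| 0.41 | 0.2 | 0.312 | 0.419 |
| 0.41 | 0.3 | 0.342 | 0.600 |
| 0.41 | 0.4 | 0.373 | 0.755 |

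The reference is 0.118 at a true 25%.

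**The case against.** The strongest reply is that Section 14.2 attaches the decision rule to major erythroid response. A platelet-only response is not erythroid, so under that text it cannot count toward 17 of 52. This stands. The probabilities in step 4 apply only if HI is substituted. The possibility remains open because the synopsis and Section 4.1.1 name HI as primary and Section 11 does not define a major erythroid response. Even if Section 14.2 governs, the reported HI rate and time to HI are still affected.

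Second, a reader might infer that any Arm B patient with a baseline below 20,000 who stays on protocol for more than 8 weeks is a responder, so that the titration target and the response are one event. The documents do not support this. The gate needs 2 weeks and HI needs more than 8. Recovery may come as late as week 8. Eltrombopag stops when lenalidomide starts, and a later fall leads to a hold and re-treatment rather than removal, so the run of consecutive weeks can break while the patient remains on study. Completing the whole duration before lenalidomide requires an early crossing and a late passage of 50,000, which is a narrow route of unknown frequency.

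Third, the inputs are weak. Section 3.2 does not define efficacy for the 41%, and the documents give neither the Arm B share nor the share below 20,000. This also stands: the size is illustrative.

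Fourth, the regimen is a planned sequence, platelet effect is already a secondary objective, and Section 14.2 plans exploratory analyses by platelet group. Counting platelet benefit of the whole strategy can be defended, but the plan should then say so and not attribute it to the combination. Those provisions do not remove eltrombopag-only responses from the primary HI rate.

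**Conclusion.** The gap is real. Sections 4.1.1 and 11 allow platelet improvement reached on eltrombopag alone to count as HI of the combination. For every baseline below 20,000 the count part of the criterion is met before the first lenalidomide dose; in some patients the duration could be met then too. For baselines of 20,001 to 49,999 the gate does not guarantee the count, but the missing exposure condition applies to them as well.

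The bias is toward a higher reported HI rate and a shorter time to HI. Its size cannot be fixed from the documents. It would be tempting to conclude that the go/no-go decision is inflated to 24–41% or 42–75%. That follows only if HI replaces the erythroid outcome of Section 14.2 and the assumptions in step 4 hold. This should be corrected before analysis, but the written erythroid decision rule is not itself affected.

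**What to change.** In Sections 4.1.1 and 11 (and the synopsis endpoint), base the combination's primary response rate on erythroid response, consistent with Section 14.2, and state which erythroid criterion is meant by major. Report HI by lineage and by drug exposure during the improvement: eltrombopag alone, lenalidomide alone, or both. Report platelet-only improvement reached on eltrombopag under the existing secondary platelet objective, and exclude it from the combination HI rate and from time to HI.

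Merely starting the 8-week window at the first lenalidomide dose would not be enough. The count would still be compared with the pre-eltrombopag value, so the lead-in rise would still be scored.

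The cost is wording. Blood counts and dosing are already followed in the trial. The downside is a somewhat lower reported HI rate.
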